- ii) In adequate patient recruitment. We anticipate recruiting an average of 4 patients per study month. If there is a significant lag and will be unable to obtain our full number of patients within a reasonable time, this will be reason to terminate the study early.
- b) Principle investigators will consider study cessation if SAEs occur within a specific treatment arm out of proportion to what would be expected from typical disease course.

Statistical Considerations

Our goal is to recruit 25 patients into each group. Given this is a pilot study, the minimum number needed per arm would be 12 patients as per published statistician recommendations [21]. The reasoning for using a pilot study include determining the feasibility of performing a larger scale study. Performing a pilot study prior to the large-scale study will give us information on patient recruitment and retention, along with design flaws that may be remedied prior to future studies.

All data will be summarized by group at each time point; summaries will include frequencies and proportions for categorical variables and mean, standard deviation, and range for continuous variables. Distributions of continuous variables will be examined. Parenteral nutrition characteristics will be recorded and tabulated. Tabulated categorical outcomes will include: proportions of subjects with cholestasis or IFALD, essential fatty acid deficiency, enteral autonomy at end of study, retinopathy of prematurity, chronic lung disease, and adverse events. Tabulated continuous measurements will include: growth rates, essential fatty acid profile, total caloric intake, percentage of calories from enteral intake, time to enteral autonomy, lipid dose delivered, bilirubin level, liver enzymes, gamma-glutamyl transferase (GGT), triglycerides, and length of stay. Fisher's Exact Tests will be used to compare between groups for categorical variables. Time to enteral autonomy will be evaluated using Kaplan-Meier survival curves and a log-rank test. Mixed models will be used to compare between groups and compare within groups over time for continuous variables measured throughout the study. Length of stay will be compared using a Wilcoxon Rank Sum test. A 5% significance level will be used for all tests mentioned.

Privacy/Confidentiality Issues

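### Time to enteral autonomy is to be tabulated by mean, SD and range, which only infants who reach autonomy can supply, and its Kaplan-Meier analysis has no rule for death.

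*Combined protocol and SAP*

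**What the plan says.** All of the analysis text is in Statistical Considerations.

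- The general summary rule prescribes "mean, standard deviation, and range for continuous variables".
- The list to which that rule applies names this endpoint: "Tabulated continuous measurements will include: growth rates, essential fatty acid profile, total caloric intake, percentage of calories from enteral intake, time to enteral autonomy".
- A later sentence gives the comparative method: "Time to enteral autonomy will be evaluated using Kaplan-Meier survival curves and a log-rank test".
- Autonomy also appears as a categorical outcome, in a list that includes "enteral autonomy at end of study, retinopathy of prematurity, chronic lung disease, and adverse events", and for such outcomes "Fisher's Exact Tests will be used to compare between groups for categorical variables".

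Elsewhere in the combined document:

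- Study Objectives (secondary item d) lists three separate quantities: the time to autonomy, glossed as full enteral feedings; the share of enteral calories at the end of the study; and the percentage of each group with autonomy. The plan therefore expects some infants not to reach it.
- The start of the clock is written only in the data list for historic controls, as the start of enteral feeding. That data collection is limited to the Riley admission.
- Stopping study Lipid and Study Duration end study lipid at 84 days at the latest, or earlier at discharge, transfer or certain other events. Follow-up after that point is itemised, and enteral autonomy is not among the items.
- Death is foreseen in Adverse Events and Serious Adverse Events, where it is grade 5. No death rate is given.

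No section says how death, transfer, discharge, withdrawal or the end of observation enters the time-to-autonomy analysis.

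**The concern.** There are two separate problems.

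The first lies in what the plan states. Time to autonomy is a time-to-event variable, and infants without the event have no value. A mean and SD must either leave them out or enter their last observed time as if it were an event. Either way the result is not the average time to autonomy. Leaving them out removes the slowest infants, so the group with more slow infants loses more of them and the groups look alike. A pilot's mean and SD are also figures that could be carried into the design of the larger study.

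The second lies in what the plan leaves out. An infant who dies before autonomy can no longer reach it. Standard Kaplan-Meier practice, absent an instruction, would censor that infant and so treat autonomy as still possible. Read as a probability, the curve would then be too high.

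**Working it through.** **No figure to reproduce.** The documents give no autonomy rate, death rate, event count or power for this endpoint. Everything below illustrates size. From the documents come the 84-day limit on study lipid and the target of 25 per arm. The distributions, the autonomy shares and the death shares are assumptions. Cutting observation of this endpoint at 84 days is also an assumption, because that limit is written for study lipid.

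**1. Mean among achievers, no deaths.** Assume Weibull times with shape 1.3 and scale s of 70 days (group A) or 110 days (group B), so S(t) = exp(−(t/s)^1.3).

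- Median = s × (ln 2)^(1/1.3) = 0.7543 × s, which is 52.8 days for A and 83.0 days for B, a difference of 30 days.
- Autonomous by day 84 = 1 − exp(−(84/s)^1.3). For A this is 1 − exp(−1.267) = 0.718. For B it is 1 − exp(−0.704) = 0.506.
- Mean among achievers = [area under S from 0 to 84 − 84 × S(84)] / [1 − S(84)].
  - A: (51.83 − 84 × 0.2815) / 0.7185 = 39.2 days.
  - B: (63.19 − 84 × 0.4945) / 0.5055 = 42.8 days.
- The difference in these means is 42.8 − 39.2 = 3.6 days.

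**2. Cross-check with a different model.** Assume a constant hazard h, 60% autonomous by day 84 and no deaths. Then h = −ln(0.40)/84 = 0.01091 per day.

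- Mean among achievers = 1/h − 84 × 0.40/0.60 = 91.7 − 56.0 = 35.7 days.
- Restricted mean to day 84, counting everyone = 0.60/h = 55.0 days.

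The bias has the same direction under this model, again without any deaths.

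**3. Kaplan-Meier if deaths are censored.** Assume proportional cause-specific hazards. Let Fa be the true share autonomous by day 84 and Fd the share dying first. Then

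1 − KM = 1 − (1 − Fa − Fd)^(Fa/(Fa + Fd)).

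With Fa = 0.60:

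| Deaths first (Fd) | Exponent | 1 − KM | Excess | Infants of 25 |
|---|---|---|---|---|
| 0 | 1.000 | 60.0% | 0 | 0 |
| 6.7% | 0.900 | 62.8% | 2.8 points | 0.7 |
| 10% | 0.857 | 64.4% | 4.4 points | 1.1 |
| 15% | 0.800 | 67.0% | 7.0 points | 1.8 |

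The standard error of a proportion of 60% in 25 infants is √(0.60 × 0.40/25) = 0.098, or about 10 points. At these death shares the excess is smaller than sampling error. Unlike sampling error, it always runs in the same direction.

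**4. Which quantiles can be reported.** In step 1 neither group reaches 75% by day 84 (72% and 51%), and in step 3 autonomy stops at 60%. The upper quartile is not reached in any of these cases.

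**The case against.** The strongest reply is that the comparison the plan relies on is largely right. Four parts of it stand.

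- Kaplan-Meier handles administrative censoring properly. Step 1 of the working contains no deaths, so the planned curves would recover the medians of 53 and 83 days. A reader might infer from the contrast of 30 days with under 4 that the planned comparison fails. It does not. The contrast concerns the descriptive table entry only.
- A reader might infer that the plan treats death as censoring. The documents do not say so. They name no rule at all, so this part is an omission with a likely default.
- A reader might also infer that the plan misreports how often infants reach full feeds. That is not supported, because the proportion with autonomy is its own secondary outcome, compared by Fisher's exact test. In step 1 it would show about 72% against 51% beside the misleading means.
- The log-rank test with deaths censored remains a valid comparison of cause-specific rates.

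What the reply does not remove is the mean, SD and range, which stay in the plan and describe speed wrongly whenever some infants do not reach autonomy under observation. The separate proportion does not correct a statement about speed. If deaths occurred and were censored, the report could also carry a curve and a proportion that disagree, with no explanation in the plan.

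**Conclusion.** The point holds in two parts of unequal strength.

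The mean, SD and range are unsuitable for this variable. That follows from the text and needs no deaths, only that some infants are not autonomous when observation ends. The size depends on the assumed distribution and the assumed 84-day cut: a 30-day difference in medians shrank to 3.6 days in the example.

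The missing rule for death is conditional. If deaths before autonomy are censored, one minus Kaplan-Meier overstates a true 60% by about 3 to 7 points when 7% to 15% die first, which is 0.7 to 1.8 infants of 25. With no such deaths there is no excess. Since the documents give no death rate, it cannot be said that the planned curve will be wrong, or that it will be more wrong in one arm than in the other.

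This is a secondary endpoint in a pilot. Neither the primary cholestasis analysis nor the sample size is affected.

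**What to change.** Amend Statistical Considerations as follows.

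1. Remove time to enteral autonomy from the measurements summarised by mean, SD and range.
2. Report the cumulative incidence of autonomy by group (Aalen-Johansen estimate) with death as a competing event. Give the median where it is reached, and quartiles only where they are reached.
3. Keep the log-rank test, labelled as a comparison of the cause-specific rate of autonomy.
4. State one time origin, one event definition and one end-of-observation rule, and apply them to prospective infants and historic controls alike. Say how transfer, discharge, withdrawal and the end of the study-lipid period are handled. If the historic data stop at the end of the Riley admission, the prospective rule has to be compatible with that.
5. Leave the separate proportion with autonomy and its Fisher's exact test as they are.

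The cost is a few sentences and standard software. No extra infants, visits or measurements are needed, provided that the end-of-observation rule stays within the data already collected.
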